National Institutes of Health (NIH)-funded investigators and clinical trial site staff who are responsible for the conduct, management, or oversight of NIH-funded clinical trials have completed Human Subjects Protection and ICH GCP Training.

The protocol, informed consent form(s), recruitment materials, and all subject materials will be submitted to the Institutional Review Board (IRB) for review and approval. Approval of both the protocol and the consent form must be obtained before any subject is enrolled. Any amendment to the protocol will require review and approval by the IRB before the changes are implemented to the study. In addition, all changes to the consent form will be IRB-approved; a determination will be made regarding whether a new consent needs to be obtained from subjects who provided consent, using a previously approved consent form.

1. PROTOCOL SUMMARY

1.1 SYNOPSIS

Title:	Mechanism of Action of Transcranial Alternating Current Stimulation for the Treatment of Major Depressive Disorder
Study Description:	The purpose of this clinical trial is to investigate the mechanism of action of non-invasive transcranial alternating current stimulation (tACS) in subjects with major depressive disorder (MDD). We will recruit 20 males and females with unipolar, non-psychotic MDD. Eligible subjects will have 5 consecutive 40-minute stimulation sessions. Subjects will be randomly assigned to one of two groups: sham stimulation or 10Hz (alpha) tACS. Participation will include 8 visits, two of them remotely. Participants will give electronic informed consent during the first remote screening sessions. At the initial stimulation session (D1), the electronic consent is printed out and handed to the participant. Eligible subjects will undergo 5 consecutive stimulation sessions with ongoing assessment of suicidality and manic symptoms. Subjects will fill in a questionnaire about stimulation side effects. Neurophysiological measures with high-density EEG will be taken before and after every stimulation session, as well as at the 2-week follow-up visit. Clinical assessments will be performed at baseline (D1), Day 5 of stimulation, and at the follow-up visit using the Hamilton Depression Rating Scale (HDRS-17). Additional assessments of symptomology, quality of life, sleep, and arousal will be completed per the research schedule and are mostly implemented as electronic surveys.
Objectives:	
Primary Objective: To investigate the physiological changes in subjects with MDD over the course of a 5-day, 40-minute stimulation protocol, specifically changes in alpha oscillation power from resting state EEG recordings over the course of the intervention (D1 to D5 of stimulation, to the follow-up visit).
 
Secondary Objectives: To elucidate the relationship between changes in EEG and changes in depressive symptoms, by comparing the changes in clinical assessments (e.g., HDRS) and the change in alpha oscillation power over the course of the intervention (baseline to day 5 of stimulation, to the follow-up visit).

Endpoints:	
Primary Endpoint: Immediate effects on resting state EEG recordings on each day of stimulation as well as long term effects 2-weeks after stimulation.
 
Secondary Endpoints: Relationship between symptoms of depression per self-report and clinician rated and physiological changes.

Study Population:	We will recruit 20 males and non-pregnant females (age 18-70) with a diagnosis of unipolar, non-psychotic MDD, free of benzodiazepines and anticonvulsant medications. Eligible subjects will have a Hamilton Depression Rating Scale (HDRS-17) > 8 and low suicide risk (determined by scoring less than 3 on the Suicide Item on the HDRS as well as having no active intent as determined by the Columbia Suicide Severity Rating Scale

(C-SSRS). Subjects will be recruited from the Chapel Hill, Durham and Raleigh areas.

Phase:

N/A

Description of

University of North Carolina at Chapel Hill.

Sites/Facilities Enrolling

Participants:

Description of Study

Intervention:

We will use the XCSITE100 stimulator designed by PulvinarNeuro for investigational purposes to deliver either active sham or 10Hz transcranial alternating current stimulation. Active sham treatment will include 20 seconds of ramp in to 40 seconds of 10Hz tACS with a ramp out of 20 seconds for a total of 80 seconds of stimulation. The choice of an active sham is motivated to enhance success of subject blinding by mimicking skin sensations associated with tACS. 10Hz tACS will also have a 20 second ramp in and ramp out with 40-minutes of stimulation for a total of 2440 seconds. Stimulation waveforms are sine-waves with a zero-to-peak amplitude of 1mA. Subjects will stay in a relaxed yet experimentally controlled state by watching a nature movie such as "Reefscape" during stimulation.

2 years

[figure not shown]
Study Duration:

Participant Duration:

[figure not shown]
Participation for each subject will last no longer than 2-3 weeks total. Completion will involve a maximum number of 8 appointments. The initial session is a remote (via Zoom) pre-screening. Participants are asked general exclusion criteria regarding brain stimulation studies and describe their mental health history. The meeting takes approx. 30 minutes. If no exclusion criteria are present, an appointment for the screening session is scheduled. This session – in person or remotely – involves the clinical assessment of depression severity (HDRS), psychiatric diagnose (M.I.N.I.) and suicidality (C-SSRS). After consultation with the study PI [name], treatment resistance is determined (Maudsley Staging Method) and participants are randomized and start the five-day stimulation procedure. The initial session (D1) and D5 will take approximately 4 hours. D2-D4 will take 90 minutes. The 2-week follow-up will take approximately 3 hours. We estimate total participation time to be approximately 17 hours.

1.2 SCHEMA

[figure not shown]
Pre-screening Session (remote)

Screening Session (remote/in person)

Stimulation Week (in person)

Daily suicidality survey emailed

2-week FU (in person)

1.3 SCHEDULE OF ACTIVITIES (SOA)

Procedures	Pre-Screening (remote)	Screening (in person / remote)	Day 1 of Stimulation (D1)	Day 2 of Stimulation (D2)	Day 3 of Stimulation (D3)	Day 4 of Stimulation (D4)	Day 5 of Stimulation (D5)	Interim Day 6-Day 21 +/-3 days	2-week Follow up (FU) Day 22 +/-3 days
Electronic Informed consent (S)	X								
HIPPA authorization			X						
Medication & Psychotherapy	X	X	X	X	X	X	X		
Determine Eligibility	X	X							
Handedness (S)	X								
Demographics + Medical Hx (S)	X								
M.I.N.I.	X								
C-SSRS	X	X					X		X
HDRS-17	X	X					X		X
WHODAS 2.0 (S)	X								
Maudsley Staging Method	X								
Randomization	X								
Urine Pregnancy Test			X						
Beliefs about Treatment (S)		X							
IDAS (S)		X					X		X
Rumination (S)		X					X		X
SHAPS (S)		X					X		X
PSQI (S)		X					X		X
BDI II (S)		X					X		X
Q-LES-Q-SF (S)		X					X		X
BAS/BIS (S)		X					X		X
STAI Y1 / Y2 (S)		X					X		X
YMRS		X					X		X
Vitals		X	X	X	X	X	X		X
EEG		X	X	X	X	X	X		X
tACS Stimulation (alpha/sham)		X	X	X	X	X	X		
Daily Stimulation Q (S)		X	X	X	X	X	X		
AE Structured Interview + Review		X	X	X	X	X	X		X
Blinding Q (subject) (S)							X		
Blinding Q (operator) (S)							X		
Symptom Improvement Q. (S)							X		
Daily Suicide Survey (S)			X-----		X-----	X-----	X-----	X-----	X-----

(S): implemented as survey in RedCap, Q is used as abbreviation for questionnaire.

Daily Suicide Surveys will be conducted in RedCap throughout the study

2. INTRODUCTION

2.1 STUDY RATIONALE

Major depressive disorder (MDD) is a common, severe psychiatric illness that affects 6.7% of adults every year in the United States [1]. MDD is characterized by depressed mood, loss of interest or pleasure in activities that used to be enjoyable (anhedonia), sleep disturbances, cognitive impairment, and other symptoms that can severely affect quality of life. Current recommended pharmacological treatments are non-targeted, resulting in undesirable side effects. Furthermore, the STAR*D trial demonstrated that a large percentage of patients are treatment-resistant, and that remission is less likely following multiple drug trials[2]. More effective and safer therapies for the treatment of MDD are desperately needed.

2.2 BACKGROUND

MDD has been associated with hypoactivity in the left dorsolateral prefrontal cortex [3], characterized by elevated alpha oscillations [4]. Therefore, targeting and reducing alpha oscillations in the left dorsolateral prefrontal cortex could prove beneficial to patients with MDD. Targeted stimulation modalities, such as transcranial alternating current stimulation (tACS), can directly engage and modulate oscillatory activity. TACS utilizes sine-wave stimulation waveforms that can enhance specific oscillatory activity [5]. The proposed study is a follow-up to a recently concluded trial run by the Carolina Center for Neurostimulation under the direction of [name] [6].

This recently published trial compared the efficacy of 10Hz-tACS (therapeutic frequency, n = 10), 40Hz-tACS (control frequency, n = 10), and sham/placebo stimulation (n = 10). The intervention consisted of 5 consecutive days of 40-minutes of stimulation. Results demonstrated that 2-weeks after completion of the intervention, the 10Hz-tACS group had more subjects responding to treatment (i.e., at least a 50% decrease in depressive symptoms) as measured by the clinician-administered assessments (Montgomery-Asberg Depression Rating Scale, p = 0.026, and Hamilton Depression Rating Scale, p = 0.026). Concurrently, we found that 10Hz-tACS successfully reduced alpha oscillations in the left frontal regions after completion of the stimulation protocol (p < 0.05). While these data demonstrate preliminary efficacy, it is unclear how tACS caused this change, indicating a need to elucidate neurophysiological mechanism of action. Previous work from other groups demonstrate an increase in alpha oscillations following tACS (e.g., [[7]–[9]]), whereas our stimulation paradigm resulted in a decrease in alpha oscillations. Importantly, what is missing is the temporal course of these physiological changes and how they correspond to clinical outcomes. By including high-definition EEG before and after each stimulation, we will be able to delineate the neurophysiological reorganization of alpha oscillations in response to repeated application of tACS.

2.3 RISK/BENEFIT ASSESSMENT

2.3.1 KNOWN POTENTIAL RISKS

Risk of Confidentiality Breach: In the unlikely event of a breach of confidentiality, people might discover that an individual was involved in this research study. This is especially sensitive because the clinical population recruited for this study may be subjected to negative consequences caused by the stigma of mental disorders. Furthermore, some might not agree with the principle of participating in research or of

changing natural brain activity. To avoid breaches in confidentiality, study documents that contain personal information, including the informed consent document, and the document that links study ID numbers to personal identifying information are kept in locked filing cabinets in locked rooms, separate from any source documents containing subject dummy identifiers. All data is stored in locked cabinets inside locked offices; electronic data will be stored only on password-protected computers, and data encryption methods will be used during communication between investigators. Interviews will be conducted over the HIPAA approved Zoom account. Only study personnel will have access to the data. All study staff participate in annual human subject training that includes education about responsibilities to the minimize risk of confidentiality breach.

Risk of Embarrassment: Self-report assessments contain questions regarding sensitive personal information. This risk is necessary in order to assess mood symptoms and associated psychopathology. Subjects will be assured upon intake that only study personnel will see any clinical ratings and that self-identifying information will not be collected alongside HIPAA protected information.

Risk of Injury and Discomfort: The side effects of tACS are mild and transient; in fact, low intensity transcranial current stimulation, such as tACS, has been used for several years without any report of serious side effects [10]. Furthermore, this stimulation mode has nothing to do with electroconvulsive therapy that applies many orders of magnitude higher stimulation current. Rather, transcranial current stimulation is so weak that it does not cause super-threshold activation of neurons [11]. However, tACS does have some mild side effects, such as transient mild tingling, burning, or itching under the electrode sites. In our previous trial, subjects from all three groups of stimulation reported either absent or mild side effects, and there was no difference between the groups with the exception of “flickering lights” (or phosphenes, $p = 0.014$)[6]. To monitor these mild side effects, we will be administering a stimulation questionnaire after each stimulation session to determine whether these effects were experienced and at what intensity. Research personnel is present during the full experimental. If subject is experiencing severe discomfort (as determined by the questionnaire or by self-report), the stimulation will be stopped immediately.

Patients with MDD have an about 20 times higher rate of suicide than average. We have no evidence that our treatment paradigms will in any way increase this likelihood. In the previous iteration of this trial, 4 subjects in the sham/placebo stimulation group experienced an increase in suicidal thoughts and only one of those 4 subjects reported suicidal intent [6]. No subjects who received tACS reported an increase in suicidal ideation from baseline. Regardless, subjects with high suicide risk will not be included in this study. If an enrolled subject shows signs of suicide risks that were not apparent during enrollment, a referral to UNC Psychiatry will be made. [name], Co-I, will facilitate this process.

We will be using the Suicide Item included in the HDRS-17 [12] to assess suicide risk, as well as the Columbia Suicide Severity Rating Scale (C-SSRS) [13] to determine intent for suicide during the screening interview. Inclusion criteria state that the subject must be low suicide risk and that potential subjects with an above “low risk” designation will not be eligible for the study. After the subject enrolls in the study, we will evaluate suicidal thoughts daily through an online questionnaire administered through REDCap. Additionally, the C-SSRS will be administered at D1, D5, and at the 2-week follow-up visit. In the event that suicide risk increases during participation in the study, the subject will be asked to stop the study. The subject will be provided with a referral to UNC Department of Psychiatry, and their mental health care or family medical doctor will be contacted.

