7. STUDY INTERVENTION DISCONTINUATION AND PARTICIPANT DISCONTINUATION/WITHDRAWAL

7.1 DISCONTINUATION OF STUDY INTERVENTION

Discontinuation from the week of stimulation does not mean discontinuation from the study, and remaining study procedures should be completed as indicated by the study protocol. If a clinically significant finding is identified (including, but not limited to changes from baseline) after enrollment, the investigator or qualified designee will determine if any change in subject management is needed.

The study intervention (i.e., the 5 consecutive days of stimulation) will be discontinued for the following reasons:

- A subject develops significantly increased suicidal risk, as determined by an acute assessment by [name] or [name].
- A subject has a YMRS score greater than or equal to 12.

- The subject misses a single day of stimulation and is unable to make it up at the end of the stimulation week.
- The subject fails to complete the online suicidality questions within 72 hours of receiving the survey email and a personal phone contact does not explain the omission.
- Any clinical adverse event (AE), laboratory abnormality, intercurrent illness or other medical condition, or situation occurs such that continued participation in the study would not be in the best interest of the subject.
- The subject meets any exclusion criteria (either newly developed or not previously recognized).

If the subject withdraws from the intervention, the subject will be contacted and invited for the 2-week follow-up assessment including all respective questionnaires. This assessment is not intended as a clinical follow-up with the participants but serves research purpose only.

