8.2 SAFETY AND OTHER ASSESSMENTS

8.2.1 SUICIDAL IDEATIONS AND SUICIDAL BEHAVIOR

Only subjects with a HDRS-17 suicidality item score of <3 and low suicide risk based on the C-SSRS are enrolled in this study. Furthermore, suicidal thoughts and behaviors will be assessed using a brief daily suicide survey (IRB# 14-0600) consisting of three questions. Participants will be asked if they had any thoughts of hurting themselves in the last 24 hours (suicidal ideation, SI) and whether they have hurt themselves in the past 24 hours (suicidal behavior, SB). They will also be asked to rate the severity of their depression on a scale of 1 to 10. Participants receive a link to answer the daily suicide survey on RedCap. To maximize participant's safety the daily suicide survey is send during the follow-up period as well. Responses will be monitored by study personnel daily and the last survey will be administered at the day of follow-up visit. In addition, the C-SSRS [13] will be administered by trained research personnel at screening, D1, D5 and the follow-up session to thoroughly assess suicide risk.

If a participant report experiencing either SI or SB on either tool, research personnel will collect more information from the participant to deliver to either [name] or [name]. Clinical personnel will decide if an acute assessment is required. Acute assessment may include facilitating contact of the subject with their psychiatrist or primary care physician to establish a plan for safety, continued care, and follow-up. If the participant does not have an established provider, [name] or [name] will assist in establishing a care plan. If at any point during the assessment, the participant is deemed an imminent risk of harm to self or others, study personnel will enlist the aid of campus security to ensure that the participant is safely escorted to the Emergency Department for further care. [name] and/or Dr.

[name] will decide if participation should be stopped after the acute assessment. If the participant is hospitalized, their participation will end.

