9.4.4 SAFETY ANALYSES

As discussed in **Section 8.2, Safety and Other Assessments** safety will be assessed with the three questions from the daily suicide questionnaire, the C-SSRS, an adverse effects questionnaire, and the Young Mania Rating Scale (YMRS).

The suicide questionnaire is used as a screening to assess increase in suicidal ideation (SI) or suicidal behavior (SB) daily. The C-SSRS will be used to assess suicide risk more thoroughly. If a participant's responses on either tool indicate SI or SB, the subject will be contacted, and an acute assessment will be completed if deemed necessary by [name] or [name] (as described above). Any verified increases in suicidal ideation will be described in counts/percentages and compared between groups using chi-square tests.

The stimulation questionnaire will be administered following every stimulation session, for a total of 5 administrations per participant. This questionnaire solicits ratings of 14 possible adverse effects associated with electrical stimulation, on a scale of 1 (absent) to 4 (severe). Paired t-tests with random effect "subject" will be calculated per adverse effect to determine if there are any differences in adverse effect severity between groups (sham/placebo, 10 Hz tACS). Severity per adverse effect will be described with mean and standard deviation.

The Young Mania Rating Scale (YMRS) will be used to assess any development of mania over the course of treatment. A YMRS score of greater than 12 indicates the possible development of a manic episode. Any subject who scores greater than 12 on the YMRS will be assessed by [name] or [name]. Any verified manic episode will be described in counts/percentages and compared between groups using a chi-square test.

The Adverse Events Structured Interview will be administered by research personnel following every stimulation session and at the follow up visit, for a total of 6 time points per participant. This interview solicits open-ended descriptions of 11 possible adverse effects a participant may experience in any clinical trial as well as one question of 'any other experiences'. Responses will be reviewed by the clinician and rated as described in **Section 8.3**. Paired t-tests will be calculated per adverse effect to determine if there are any differences in adverse effect severity between groups (sham/placebo, 10 Hz tACS). Severity per adverse effect will be described with mean and standard deviation.3.

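### Section 2.3.1 conflicts with 7.1, 8.2.1 and 10.1.6 on what happens when suicide risk rises; separately, 9.3 leaves early stoppers out of the only analysis set

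*Combined protocol and SAP*

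**What the plan says.** **Stopping for suicide risk.** Section 2.3.1 says: "In the event that suicide risk increases during participation in the study, the subject will be asked to stop the study". It adds a referral to psychiatry and contact with the subject's own doctor.

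Section 7.1 discontinues stimulation when "A subject develops significantly increased suicidal risk, as determined by an acute assessment by" one of two named people. It separates this from leaving the study: "remaining study procedures should be completed as indicated by the study protocol", and "the subject will be contacted and invited for the 2-week follow-up assessment including all respective questionnaires".

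In section 8.2.1, clinical personnel first judge whether an acute assessment is needed. Two named people then "will decide if participation should be stopped after the acute assessment". One event is automatic: "If the participant is hospitalized, their participation will end". For safety, "the daily suicide survey is send during the follow-up period as well".

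Section 9.4.4 repeats that "an acute assessment will be completed if deemed necessary by" the named people. Section 10.1.6 has the PI review changes in suicidality ratings, and continuation depends on that review.

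**Analysis set.** Section 9.3 describes a modified intention-to-treat set, but the condition for entry is receiving all five days of stimulation. Sections 7.2 and 9.3 replace randomised subjects who receive only part of the intervention. Section 9.4.2 allows a repeated-measures ANOVA, a mixed model (GLMM) or both, and prefers the GLMM when data are missing.

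**The concern.** A suicide-risk rule should have one reading. Staff who follow 2.3.1 literally could take a subject out of the study just when risk has risen. The daily survey and the follow-up C-SSRS are study procedures and would be expected to end with participation.

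The analysis-set point is distinct and does not depend on how 2.3.1 is worded. A randomised subject who stops before session five, for suicidality or anything else, drops out of the primary EEG comparison and the EEG–HDRS correlation. The reason may be linked to the disease or to the arm, and that weakens the protection randomisation gives.

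**Working it through.** The plan states no figure on this point, so there is none to reproduce. The first part is a comparison of text.

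| Section | Trigger | Who decides | What stops |
|---|---|---|---|
| 2.3.1 | Any increase in risk | Not stated | The study |
| 7.1 | Significantly increased risk at an acute assessment | One of two named people | Stimulation only; follow-up kept |
| 8.2.1 | Ideation or behavior reported; acute assessment if judged necessary | Clinical personnel, then two named people | Participation, at their discretion; automatic on hospitalization |
| 10.1.6 | Change in suicidality ratings | PI | Participation, on review |

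Take a subject who reports new ideation without intent on day 3. Under 2.3.1 the subject is asked to leave the study. Under 7.1 stimulation goes on unless an acute assessment finds significantly increased risk, and follow-up is kept even then. Under 8.2.1 there may be no acute assessment, and if there is one, participation may or may not stop. The sections differ on trigger, decision-maker and scope.

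**Who leaves the analysis set.** Completion is the entry condition in 9.3 and non-completers are replaced. The exclusion is therefore implied, not stated. It reaches those who stop before the fifth session; a subject stopped after day 5 stays in. Section 9.4.4 names no separate safety population.

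**How many.** Inputs: in the earlier trial 32 enrolled and 30 completed five days (9.2); 4 sham subjects had increased suicidal thoughts and no tACS subject did (2.3.1).
- Non-completers: 32 − 30 = 2, and 2/32 = 6.25%, with exact (Clopper–Pearson) 95% limits 0.8% to 20.8%. This covers three arms and any reason.
- Assuming the same rate here: 20 × 0.0625 = 1.25 subjects, with limits 20 × 0.0077 = 0.15 to 20 × 0.2081 = 4.16.
- If all 4 sham subjects were among the 32, at least 4 − 2 = 2 of them finished all sessions.

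**Cost of including early stoppers.** Suppose k partly treated active subjects with no effect at all join 10 completers and supply follow-up EEG. The mean follow-up effect is then 10/(10 + k) of its full size:
- k = 1: 10/11 = 91%
- k = 2: 10/12 = 83%
- k = 4: 10/14 = 71%

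The last case takes the upper limit of about 4 in 20 and puts all of them in the active arm. A subject with baseline EEG only adds little.

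**The case against.** **2.3.1 is only a risk narrative.** The operative procedures are in 7.1 and 8.2.1, which are detailed and name who decides. That limits the weight of the conflict, but 2.3.1 still states an action, carries no cross-reference and is stricter than the operative text.

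**A reader might infer that 2.3.1 acts without any assessment.** The sentences before it describe the low-risk designation, the daily questionnaire and repeated C-SSRS, so the increase may be one found by those tools. What is missing is a threshold and a decision-maker.

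**A reader might infer that 2.3.1 alone is out of line.** It is not. Sections 8.2.1 and 10.1.6 speak of stopping participation, whereas 7.1 stops stimulation, so these sections also differ on scope.

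**A reader might infer that a subject stopped under 2.3.1 loses all safety follow-up.** The documents do not support that. Referral and doctor contact remain. Section 8.3.4 records deterioration as an adverse event, follows events to resolution or stabilization, and records SAEs for 30 days after participation.

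**A completer set is defensible here.** This is a 20-subject pilot on mechanism, and the set was declared in advance. That is arguable, but the set is then misnamed and is the only one defined. It is also true that the remedy may miss some of the cases behind it: a hospitalized subject's participation ends, so there may be no later EEG.

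**Conclusion.** Both parts hold, and neither is large.

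1. The suicide-risk rules conflict on trigger, decision-maker and scope. Section 2.3.1 is wrong as written; the repair is a minor consistency correction. The practical risk is losing the daily survey and the follow-up C-SSRS, not losing all care.
2. The 9.3 set is a completer set under another name. Changing it is a cheap improvement. Correcting 2.3.1 does not remove this weakness, although the stopping rule affects how many subjects are lost.

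It is tempting to read the 4 sham events against none on tACS as showing that exclusion would fall on sham and bias the result in a known direction. The documents do not support this. Only 2 of 32 failed to complete, and their arms and reasons, the timing of the suicidality events and the earlier trial's stopping rule are not given. The figure of about 1.3 early stoppers in 20 (0.2 to 4.2) assumes the earlier rate carries over and counts all reasons, not suicidality alone.

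**What to change.** **Section 2.3.1.** Replace the sentence with: *If suicide risk increases, Sections 7.1, 8.2.1 and 10.1.6 apply: clinical personnel judge whether an acute assessment is needed; stimulation stops if that assessment finds significantly increased risk; study participation ends only on hospitalization or by decision of the study clinician or PI; otherwise safety monitoring and the 2-week follow-up continue.* Keep the sentence on referral and doctor contact. This leaves the acute assessment discretionary, as 8.2.1 and 9.4.4 have it.

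**Section 9.3.** Define the primary set as all randomised subjects who received any session, active or sham, analysed as randomised. Show five-session completers as a sensitivity analysis. Keep replacement, with replaced subjects remaining in the analysis.

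**Section 9.4.2.** Drop the ANOVA alternative and name the GLMM, fitted to all available baseline, day 5 and follow-up EEG.

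**Cost.** One sentence, one paragraph and one phrase, in a single IRB-approved amendment made before unblinding. The 9.3 and 9.4.2 changes alter the primary analysis, so they are more than wording, and they carry the dilution shown above. They add no enrolment, visits or staff: non-completers are already replaced and already invited back, and the GLMM is already allowed. The 2.3.1 correction can go ahead even if the analysis-set change is declined.
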